## **5.5 Clinical Experience with Vaccines Derived from the Same Genotypic Strain**

As detailed in Section 5.3.1, SRL 172 was a heat-inactivated, whole-cell vaccine derived from a rough variant of an environmental mycobacterium. Lot MV 001 of SRL 172 was used for a series of six human studies described below (Table 5-5). All doses were administered as an 0.1 mL intradermal injection over the deltoid containing 1 mg SRL 172 in borate buffered saline (estimated to represent  $10^9$  colony forming units based on wet weight). All studies were investigator-initiated, conducted in accordance with applicable regulatory requirements, and published in peer-review journals as indicated.

**Table 5-5. Studies conducted using SRL 172 (Lot MV 001)**

Study Number	Title	Reference
001	A Phase 1 Study of Five Doses of SRL 172 in Healthy Adults	(5, 6)
002	A Phase 1 Study of Five Doses of SRL 172 in HIV-infected Adults	(7)
003	A Phase 1 Randomized, Controlled, Phase 2 Study of Three Doses of SRL 172 in HIV-infected Children	(8)
004	A Phase 2 Open-Label, Controlled Study of Five Doses of SRL 172 in BCG-positive and BCG-negative, HIV-infected Adults in Zambia	(9)
005	A Phase 2 Randomized, Controlled Trial of Five Doses of SRL 172 in HIV-negative, BCG-positive and HIV- positive, BCG-positive Adults in Finland	(10)
006	A Phase 3, Randomized, Placebo-Controlled Trial of Five Doses of SRL 172 for Protection against Tuberculosis in BCG-primed, HIV-infected Adults in Tanzania (the DarDar Trial)	(3)

**Table 5-6. Key characteristics of studies conducted using SRL 172 (Lot MV 001)**

Study Number	Period Conducted	HIV status	BCG status	N SRL 172 a	N PLA	No. Doses	Dosing (months)
001	1994–1995	Neg	Neg b	10	–	5 c	0, 2, 10, 16, 18
002	1995	Pos	Neg	12	–	5 d	0, 2, 4, 25, 26
003 e	1994–1997	Pos	Neg	23	12 f	3	0, 2, 4
004	1996	Pos	Neg	11	11	5	0, 2, 4, 12, 16
			Pos	11	11		
005	1997	Neg	Pos	10	–	5	0, 2, 4, 6, 12
			Pos	19	20 f		
006	2001–2008	Pos	Pos	1006	1007	5	0, 2, 4, 6, 12

a. In all adult studies the dose of SRL 172 was 1 mg / 0.1 mL administered intradermally in the deltoid (dose for children < 5 was 0.05 mL).

b. 1 subject was BCG-positive.

c. 3 subjects received only 3 doses.

d. 4 subjects received only 3 doses.

e. Study 003 was conducted in children (ages 6 mo to 13 yr). All other studies were in adults, ages 18 to 70 yr.

f. Controls received hepatitis B vaccine.

### 5.5.2 SRL 172, Study 002 (United States)

Study overview:

- Subjects: 12 HIV-infected adults, CD4  $\geq 300$  in US; all BCG-negative
- HIV-related characteristics: 3 on ART (1 or 2 drugs) at baseline, 5 on ART by end of study
- Dose schedule: 0, 2, 4 mos (12 subjects); 25 and 26 months (8 subjects)

Vaccine site reactions: Assessed at 2d, 14 d, 2 mos after each dose.

- Induration: maximum at 2 days, median 6 mm

Safety:

- Temperature was recorded daily at home for 14 days after each dose. All were normal,
- No systemic side effects were reported after any dose.
- CD4: Mean change from baseline to post-dose 3 was +28 (range: -137 to +137)
- HIV viral load: Mean  $\log_{10}$  change from baseline to post-dose 3 was + 0.4 (range: -0.3 to +1.5)

Immunogenicity:

- Lymphocyte proliferation:
  - SRL 172: Four subjects had stimulation index  $>2$  after dose 3 (baseline not available)
  - *M. avium* sonicate: No increases in response from baseline to post-dose 3.
- Antibody to MTB LAM: No change in antibody titer

Four patients were lost to follow-up. Among the 8 subjects who received 2 additional doses at 25 and 26 months:

- Erythema with or without induration: 4 (50%) of 8 patients (diameter not available).
- No systemic symptoms were reported.
- Stimulation indices to SRL 172 and *M. avium* were generally higher in vaccine recipients than in 7 unimmunized HIV-positive controls.

### 5.5.3 SRL 172, Study 003 (United States)

Study overview:

- Subjects: 35 HIV-infected children, ages 6 mo to 13 yr
- Subject characteristics: CD4  $\geq 300$ , age 1-8; ART encouraged (data not available)
- Treatments: 23, SRL 172; 12, intradermal hepatitis B (control)
- Dose schedule: 0, 2, 4 mos

Vaccine site reactions:

- median induration, 5 mm at 2 days; 3 mm at 14 days; 0 mm at 2 mos; 2 subjects had 4-5 mm induration at end of study (1 at dose one site, 1 at dose two site)
- crusting: present after 2 (3%) of 68 doses
- “sore arm” reported after 19 (28%) of 68 doses

Safety:

- Fever: recorded after 9 (13%) of 68 SRL 172 doses vs 3 (9%) of 35 HB doses
- CD4: median change SRL 172 = -99, HB = + 89 [ $p=0.50$ ]
- Viral load: median change = - 0.1  $\log_{10}$  in both groups

Immunogenicity:

- 1 SRL 172 recipient had 2x increase in Ab to LAM; no subjects had increased lymphocyte proliferation response to LAM

#### 5.5.4 SRL 172, Study 004 (Zambia)

Study overview:

- Subjects: 44 HIV-infected adults in Zambia, CD4; 22 BCG positive, 22 BCG negative; 31 male, 13 female; ages 21 to 51 yr.
- HIV characteristics: CD4  $\geq$ 200; none on ART
- Study design: open label
- Treatment, N, BCG status, and Dose schedule
  - SRL 172: 11 BCG-pos, 11 BCG-neg; 0, 2, 4, 12, 14 mo (5 doses)
  - borate buffered saline (control): 11 BCG-pos, 11 BCG-neg; 12, 14 mo only (2 doses)

Vaccine site reactions:

- induration
  - BCG pos: range over doses one to four: 11-14 mm at 2d, 0-3 mm at 14d; after dose five: median 5 mm at 2d, 3 mm at 14d
  - BCG neg: range over doses one to four: 8-11 mm at 2d, 0-3 mm at 14d; after dose five: median 6 mm at 2d, 3 mm at 14d
- drainage after 3 (3%) of 110 doses
- sore arm after 4 (4%) of 110 doses,

Safety:

- Temperature (measured daily for 15 days by subjects using digital thermometer): not fever noted
- Other symptoms: headache after 3 (3%) of 110 doses; malaise after 1 (0.9%) of 110 doses
- Viral load:
  - BCG neg: pre-dose 4 to post-dose 5: no significant differences compared to controls
  - BCG pos: baseline to post-dose 3, 0.5 log decrease ( $p=0.007$ ); pre-dose 4 to post-dose 5: no significant differences compared to controls

Immunogenicity:

**Table 5-7. Change in median lymphocyte stimulation index to SRL 172 sonicate, pre-dose 4 to post-dose 5**

	SRL 172	Control	p-value
BCG negative	incr: 2.3 $\rightarrow$ 6.0	decr: 3.7 to 2.6	<0.05
BCG positive	incr: 4.3 $\rightarrow$ 8.8	unch: 1.9 to 1.9	<0.001

**Table 5-8. SRL 172, Study 005: Characteristics, Safety, and Immunogenicity of HIV-positive Subjects by Treatment Group**

Characteristics	SRL 172	Control Vaccine (CV) a
N	19 b	20
Male (N, %)	17 (89%)	18 (80%)
Age (median)	40 yr	41 yr
HIV status	HIV-positive	HIV-positive
Combination anti-retroviral therapy	17	10
CD4 (median)	559 /mm 	631 /mm 
Safety		
ISR: induration 2d medians (range)	4-7 mm (0-30)	0-10
ISR: erythema 2d means (range)	10-17 mm (5-26 mm)	0-3 mm (0-10)
ISR: skin breakdown	11 – 37% post each dose	10 – 30% post each dose
ISR: drainage	5 – 11% post each dose	0 – 5% post each dose
ISR: sterile abscess	1 (5%)	0
ISR: “sore arm”	16 – 37% post each dose	10 – 30% post each dose
Fever	5% post each dose	5% post each dose
Adenopathy	5% post each dose	5% post each dose
Malaise	5 – 11% post each dose	5 – 11% post each dose
CD4 count (2 mo after dose 5)	no change from baseline no significant diff c/w CV	no change from baseline
HIV viral load (2 mo after dose 5)	no change from baseline no significant diff c/w CV	no change from baseline
Serious adverse events		
Discontinuations b	0	0
After 3 doses	2	
After 4 doses	3	
Immunogenicity		
LPA to SRL 172 sonicate	increased c/w CV post dose 3, dose 5 and 1 year	
LPA to SRL 172 sonicate	post dose 5: median cpm 12,560 vs 22,547 in HIV-neg; p=0.17	
LPA to MTB sonicate	increased c/w CV post dose 3	
IFN-γ to SRL 172 sonicate	increased c/w CV post dose 3, dose 5 and 1 year	
IFN-γ to MTB sonicate	no significant difference c/w CV	

a. CV = intradermal hepatitis B vaccine at 0, 2, and 12 mo; borate buffered saline at 4 and 6 mo.

b. Five subjects withdrew due to adverse events: one each with (a) injection site sterile abscess post dose 4; patient had apical scarring consistent with prior TB; (b) injection site induration and drainage post dose 3; (c) injection site prolonged drainage post dose 3; and (d) musculoskeletal pain, temporally related to immunization after dose 4 and (e) arthralgias after dose 4..

### 5.5.6 SRL 172, Study 006 (DarDar Trial, Tanzania)

The DarDar Trial of SRL 172 was a 7-year Phase III, randomized, controlled, GCP-compliant trial conducted in Dar es Salaam, Tanzania, initiated in 2001, and sponsored by the National Institutes of Health ([name], Principal Investigator).

Study overview (Table 5-9):

- Subjects: HIV infected adults (age  $\geq 18$ ) with prior BCG (by scar) and CD4  $\geq 200$
- N: 2013; randomized (1:1) to SRL 172 (V) or placebo (P; borate-buffered saline)
- Dose schedule: 0, 2, 4, 6, and 12 mo (5 doses)
- Follow-up: Seen every 3 months; median 3.3 years.

- Endpoints – all reviewed by a blinded 3-person expert panel using pre-defined criteria.
  - Primary endpoint: disseminated tuberculosis with positive blood culture
  - Secondary endpoint: definite tuberculosis (all culture-positive tuberculosis)

**Results.** SRL 172 was safe, well-tolerated, and induced T cell responses against the vaccine antigen and antibody to lipoarabinomannan. The trial was stopped at 7 years when the Data Safety Board determined that the vaccine was effective based on a significant reduction in all culture positive tuberculosis and a trend in the reduction of disseminated tuberculosis.

**Table 5-9. SRL 172, Study 006 (DarDar Trial): Subject Characteristics and Outcomes by Treatment Group**

NS, P value not significant; NSD, no significant difference.

NC, P value not significant, NSD, no significant difference.

1. ISR data are median (range) for all doses at day +28 post-dosing unless otherwise indicated. Maximum reactions typically after dose 3.
2. Data from Substudy A (162 subjects). CD4 and viral load change is from baseline to 2 mos post-dose 5
3. Injection site sterile abscesses occurred after the first dose in one patient and after the third dose in two patients (both with a history of prior TB); all abscesses drained spontaneously and resolved with routine wound care and oral antibiotic therapy.
4. None considered related to immunization.
5. Immunization was discontinued by the MD investigator in 12 (1.2%) subjects because of adverse reactions considered possibly or probably vaccine-related: 3 vaccine site abscesses five other local reactions and four generalized rashes. An additional 65 subjects (35 SRL-172, 30 placebo) withdrew themselves from the trial

before completing the trial citing a switch to alternative medicine, perceived vaccine side effects or inconvenience. All reactions were considered mild or moderate and resolved after discontinuation of immunization.

6. Immunogenicity assay results compare (a) baseline to post-dose 5 among SRL 172 recipients; (b) SRL 172 vs Placebo, post-dose 5. Only significant effects noted, defined as  $p \leq 0.05$ . NSD, no significant difference
7. Vaccine efficacy endpoints were prospectively defined; data were reviewed and outcomes assigned by blinded expert panel.
8. Disseminated TB, defined as a positive blood culture (Primary Endpoint). Definite TB, stringent laboratory-defined criteria (Secondary Endpoint). Probable TB, lesser laboratory findings or only clinical findings.

## 6. OBJECTIVES

### 6.1 Primary:

To evaluate the safety and efficacy of a 3-injection series of DAR-901 booster in preventing tuberculosis infection among healthy adolescents

### 6.2 Secondary:

To identify risk factors for infection with *M. tuberculosis* among healthy adolescents

To identify subject characteristics associated with vaccine induced protection against infection with TB.

## 7. INVESTIGATIONAL PLAN

### 7.1 Overall Study Design

Overall study design is presented in Section 2.4, including

- Dose Groups
- Enrollment Process
- Study Structure
- Potential protocol adjustments
- Risk Management

### 7.2 Rationale for Treatment Regimens

#### 7.2.1 Dose Level

The dose level (1 mg per dose) is based on

- the safety and immunogenicity observed in DAR-901 MDES study (see 5.4.1 )
- prior clinical experience with SRL172, a killed whole-cell vaccine prepared from the same genotypic strain grown on agar (see 5.5), and
- mouse immunogenicity studies conducted with DAR-901 (see 5.3.3 )

**Clinical studies with SRL172.** All clinical studies by Dartmouth investigators were conducted with an adult intradermal dose of 1 mg in a volume of 0.1mL (dose in children < 5 = 0.05 mL). This dose was established in initial studies by British investigators using vaccine prepared by SR Pharma (London). In the DarDar Trial of HIV-infected patients this dose was found to be safe, immunogenic, and effective in the prevention of tuberculosis (see Section 5.5.6). This will be the dose of DAR-901 in the present Phase 2 study.

#### 7.2.2 Dose Number and Dosing Interval

The dose number and dosing interval are based on

- the safety and immunogenicity observed in DAR-901 MDES study (see 5.4.1 )
- prior experience with SRL172, a killed whole-cell vaccine prepared from the same genotypic strain grown on agar (see 5.5 ), and
- published experience with other inactivated, whole-cell vaccines

**Dose number.** Inactivated whole cell vaccines are typically administered in a 2- or 3-dose schedule. A 3 dose schedule was safe and well tolerated in the DAR-901 MDES study and produced injection site reactions comparable to those observed in studies with SRL-172. Studies by Dartmouth investigators with SRL172 have shown safety and immunogenicity with both a 3-dose (Study 005, Table 5-8) and 5-dose schedule (Study 006, Table 5-9). A 3 dose schedule will be employed in the present study.

**Dosing interval.** Two month intervals between doses was safe and well tolerated in the DAR-901 MDES study and produced injection site reactions comparable to those observed in studies with SRL-172 (see Table 4) Prior studies by Dartmouth investigators with SRL-172 have used 2 month dosing intervals for 3 doses or the first 3 doses (Studies 002-006, Table 5-6). Safety and immunogenicity have been demonstrated with a 3-dose schedule at 0, 2 and 4 mos (Study 005, Table 5-8)

### 7.3 Rationale for Study Design

The study design – randomized, placebo-controlled, double-blind – is consistent with both the study objectives and current principles for the evaluation of multiple dose courses of investigational treatments. In particular, double-blinding avoids bias by the Investigator and subjects in assessing the subjective aspects of the study, particularly adverse events.

## 7.4 Maximum Exposures and Maximum Number of Subjects

The maximum exposures to DAR-901, the investigational agent, will be:

- Dose level: 1 mg per dose
- Number of doses: 3 doses over 4 months (120 days)
- Number of subjects: 650 IGRA-negative subjects

## 7.5 Definitions Applicable to Managing the Study

Treatment-emergent is defined as onset after active engagement in the trial; that is, after the administration of the first injection of study treatment. It is anticipated that treatment-related events may be observed after each injection of study treatment.

### 7.5.1 Definition of a Dose-Limiting Toxicity (DLT) Event

A DLT *systemic clinical event* is defined as a treatment-emergent systemic clinical event that meets **all** of the following criteria:

- is assessed by the investigator as related or possibly related to study drug (see Section 12.3.3);
- is of severity (see Section 12.3.4) Grade 2 or higher;
- is of duration >48 hours.

A DLT *injection site reaction* (ISR) is defined as an event that meets **both** of the following criteria:

- occurs at the injection site;
- is of severity Grade 3 or higher.

A DLT *laboratory event* is defined as a confirmed, treatment-emergent laboratory finding that meets **both** of the following criteria:

- is **not** considered consistent with a concurrent clinical event that is assessed as not related or unlikely related to study drug (e.g., an accidental injury, new ART); **and**
- based on pre-specified toxicity criteria (see Section xx) represents an increase of two Grades or more compared to pre-treatment baseline value.

A subject who experiences a DLT event will not receive further doses of study drug. Unblinding may be performed to determine if a DLT event has occurred in a subject receiving DAR-901.

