#### **12.5.1 Definitions of the Most Commonly Expected Systemic Vaccine-related Symptoms**

- Fever: elevated temperature documented by any route during a visit or by the subject at home.
- Feverish: subjective fever reported by the subject, but not documented.

- Malaise, myalgia, “flu-like” symptoms: will be defined consistent with routine clinical practice.

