#### **12.5.4 Visit Assessment of Injection Site Reactions and Other Post-Dosing Events**

At each visit specified in Sections 2.9 and 12.2, the subject will have vital signs obtained, and be interviewed by study personnel regarding symptoms and other events.

Treatment-emergent changes in vital signs will be graded using the criteria shown in Table 18-2, which are taken from FDA Guidance (13).

Subjects will be explicitly asked about systemic and local symptoms (see Sections 12.5.1 and 12.5.2, respectively), any interference with daily activities, and any treatment required. Symptoms will be graded using the functional criteria shown in Table 12-4.

Study personnel (RN or MD) will examine all of the prior injection sites and then:

- Record the presence or absence of the physical findings defined in Section 12.5.3;
- For any findings present, record the maximum linear diameter in mm;
- Pain, erythema, and induration will be graded as shown in Table 12-5, taken from FDA Guidance (13); other ISRs characteristics will be graded using the functional criteria shown in Table 12-4.
- Considering *all* the findings present, a study MD will grade the *overall* intensity (severity) of the ISR as per Table 12-4.
- This grade should be “static”, that is, based upon the impact and management of the ISR at the time, without reference to previous observations for the subject.
- Subjects will be asked for permission to photograph the ISR if it is assessed as Grade 2 or higher, is accompanied by systemic symptoms, is managed with prescription medication (e.g., systemic antibiotics or prescription analgesics) or is judged by the Investigator to warrant documentation. Photographs are completely optional and may be declined by the subject without impacting any other aspects of the protocol.

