**Table 12-4. Grading of Vaccine-Related Adverse Events**

Characteristic	Grade 1	Grade 2	Grade 3
Impact on ADL	No limitations in ADL	Some limitations in age-appropriate instrumental ADL	Some limitations in self-care ADL
Medication intervention	None or self-medication with OTC meds	Prescription meds offered; provide relief	Requires prescription meds; relief may be partial
Interventions other than medication	Minimal, local, or non-invasive	Minimal, local, or non-invasive	Requires hospital facilities for <24 hr

This Table is intended to provide guidance; the investigator should use judgment in assigning an intensity grade to an ISR. In some instances a single characteristic may determine the grade; in other instances, the overall pattern may be considered more appropriate.

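### Section 7.5.1 makes every systemic DLT last more than 48 hours, so a brief related Grade 4 event, SAE or functional Grade 3 reaction triggers no mandatory stop

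*Protocol*

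**What the plan says.** Section 7.5.1 of the protocol sets three kinds of DLT.

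- **Systemic clinical event.** All of: related or possibly related by investigator assessment; "is of severity (see Section 12.3.4) Grade 2 or higher"; and "is of duration >48 hours".
- **Injection-site reaction.** Grade 3 or higher. No duration condition.
- **Laboratory event.** A confirmed rise of two grades or more over baseline, not explained by an unrelated clinical event. No minimum duration.

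The consequence is mandatory: "A subject who experiences a DLT event will not receive further doses of study drug".

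Grades come from several places. Section 7.5.1 points to 12.3.4 and its Table 12-2. For post-dose assessment, section 12.5.4 says of systemic and local symptoms: "Symptoms will be graded using the functional criteria shown in Table 12-4". Of vital signs it says: "Treatment-emergent changes in vital signs will be graded using the criteria shown in Table 18-2". Neither Table 12-4 nor Table 18-2 has a duration element. Section 12.5.1 puts fever first among the expected systemic vaccine-related symptoms: "Fever: elevated temperature documented by any route during a visit or by the subject at home".

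**The concern.** A stopping rule should catch the events after which one would least want to give another dose. Here the time condition, which sensibly screens out short Grade 2 events, also screens out short Grade 3 and Grade 4 events. An acute systemic reaction to an injection can be severe and still resolve within two days.

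The subjects are healthy 13-15 year olds who may be due up to two further doses. For these brief severe events no rule forbids the next dose. Section 7.5.1 gives no reason why a brief Grade 3 systemic reaction should be treated more leniently than a brief Grade 3 reaction on the arm. The point concerns subject safety; it does not touch the efficacy endpoint or its analysis.

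**Working it through.** No sample-size or power figure bears on this, so the check is one of logic.

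**Step 1. The rule.** For a treatment-emergent systemic event with relatedness R, grade G and duration T:

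mandatory stop = R (related or possibly related) AND G ≥ 2 AND T > 48 h.

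**Step 2. Can G be 3 or 4 while T is 48 h or less?** Table 12-2 has a duration row: Grade 1 is typically under 48 h and Grade 3 is over two weeks. If duration always set the grade, brief Grade 3 events could not exist. It does not:

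- Section 12.3.4 calls the table guidance and allows one characteristic to decide the grade.
- Section 12.3.4.1 gives a Grade 3, non-serious example that lasts hours (a migraine attack).
- Table 12-4 gives Grade 3 for "Some limitations in self-care ADL" or "Requires hospital facilities for <24 hr", whatever the duration.
- Table 18-2 grades fever by temperature alone: 38.5-38.9 °C is Grade 2, 39.0-40 °C is Grade 3 and above 40 °C is Grade 4.
- Section 12.1.3 counts allergic bronchospasm needing intensive emergency treatment as an SAE. Section 12.3.4.1 says that medically important SAEs are typically Grade 3 or 4.

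For an event graded on duration, the 48-hour condition adds almost nothing, because Grade 2 by duration already means longer than about 48 h. It does independent work only where function, temperature or intervention sets the grade, and that is where brief severe events arise.

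**Step 3. Apply the rule.** All events are taken as related or possibly related. The last column is the rule proposed under the fix.

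| Event | Grade | Duration | Mandatory stop now? | Under the fix |
|---|---|---|---|---|
| Fever 38.5-38.9 °C | 2 | 49 h | Yes | Stop |
| Fever above 40 °C | 4 | 47 h | No | Stop |
| Bronchospasm, emergency treatment (SAE) | 3 or 4 | Hours | No | Stop |
| Flu-like symptoms limiting self-care | 3 | 24 h | No | Stop |
| Same symptoms | 3 | 72 h | Yes | Stop |
| Fever 39.0-40 °C, no functional Grade 3 | 3 | 24 h | No | Medical Monitor review |
| Symptom limiting instrumental activities only | 2 | 24 h | No | No |
| Injection-site reaction | 3 | Any | Yes | Stop (unchanged) |

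**Step 4. What else could prevent the next dose?**

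- Section 7.6.1: the investigator may stop for any adverse event. This is optional.
- Section 12.3.5: the action taken with study drug is recorded for each adverse event. This is documentation.
- Table 12-2: for related Grade 4 events the typical action is discontinuation; for Grade 3, study treatment may be discontinued. This is guidance.
- Section 7.7: the DSMB promptly reviews SAEs and makes recommendations. Non-serious events fall outside that prompt review, and section 12.1.3 generally keeps admissions under 24 hours out of the hospitalization criterion.

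None of these is a mandatory stop.

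**The case against.** Requiring both severity and persistence is a legitimate form of rule, and much of the case for it stands.

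- **Inversion.** Comparing the 49-hour Grade 2 fever with the 47-hour Grade 4 fever, a reader might infer that the rule is upside down. It is not. At any fixed duration it never treats a higher grade more leniently: past 48 h, Grades 2, 3 and 4 all stop, and at or below 48 h none does. The defect is that a severe grade never overrides the time condition.
- **The grading scale that 7.5.1 cites includes duration.** This makes brief Grade 3 events less common, not impossible (step 2). The protocol's own brief Grade 3 example is a habitual migraine rather than a drug reaction.
- **Fever above 40 °C is partly covered.** Table 12-2 points to discontinuation for related Grade 4 events, so it would be too strong to say that judgment alone decides. It remains guidance and not the 7.5.1 stop.
- **Short hospital care can still be an SAE** as an important medical event, which brings DSMB review. That review advises; it does not stop dosing by rule.
- **There is time to act.** Doses are two months apart, there is a visit about day 7 after each, and adverse events are actively sought at all study visits (12.2).
- **A blanket Grade 3 stop would overreach.** A short fever of 39.0-40 °C that is only possibly related, a category that includes another cause being equally likely, would end vaccination permanently. This objection is sound, and the fix allows for it.

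A reader might also try to size the gap from the DarDar trial, where four investigator stops were for generalized rash: 4/1006 = 0.40% (exact 95% CI 0.11-1.01%), or about 1.3 of 325 DAR-901 recipients. The documents do not support that use. Those reactions were mild or moderate, in HIV-infected adults on a five-dose course of a different preparation. They do not count brief Grade 3 or 4 events.

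**Conclusion.** The gap is real but narrow. As written, a related Grade 4 event, a related SAE or a functionally Grade 3 systemic reaction that resolves within 48 hours does not meet the only adverse-event rule that ends dosing automatically. A related Grade 2 event beyond 48 hours does meet it, and a Grade 3 injection-site reaction meets it at any duration.

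Its frequency cannot be computed from the protocol. The Phase I summary in section 5.4.1 (41 DAR-901 recipients in Table 3) reports no SAEs, and only transient low-grade fever in subjects presumed to have received BCG. That suggests few subjects would be affected, though 41 recipients cannot exclude uncommon events.

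The conclusion assumes that the event is judged related or possibly related and that something other than duration sets its grade. It does not say that such subjects would be dosed again: investigators would probably stop many of them. It says that the protocol does not require it. This is a cheap improvement rather than a fault that threatens the trial.

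**What to change.** Reword the systemic part of section 7.5.1. A systemic DLT is a treatment-emergent systemic clinical event, related or possibly related to study drug, that is:

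- (a) Grade 4 or an SAE, at any duration; or
- (b) Grade 3 by functional criteria (Table 12-2 or 12-4), at any duration; or
- (c) Grade 2 or higher and lasting more than 48 hours.

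Add that two situations go to Medical Monitor review before the next dose instead of an automatic permanent stop: a Grade 3 vital-sign reading alone (including fever of 39.0-40 °C) that resolves within 48 hours; and an isolated, asymptomatic heart rate, blood pressure or respiratory rate reading of any grade that is not confirmed on repeat. Section 7.6.1 needs no change, since it already lists a DLT as a reason to discontinue.

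The cost is one reworded definition, site retraining and an occasional Medical Monitor review; no visits, tests or subjects are added. The downside is a few more subjects stopped early, with correspondingly less vaccine exposure in the as-randomized comparison. Section 7.5.2 already counts a DAR-901 recipient stopped for a DLT as complete. If dosing had ended by version 1.4, which the protocol does not state, the wording should go into later DAR-901 protocols.
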